1.0 BACKGROUND AND RATIONALE

1.1 Study Synopsis

Increasing the sensitivity and specificity of diagnostic imaging in patients at high risk for breast or thyroid cancer could provide substantial clinical benefit by improving diagnosis, preventing over-treatment, and reducing healthcare costs. Contrast enhanced super-resolution (CESR) imaging is a new type of contrast enhanced ultrasound imaging which is specifically sensitive to microvascular structure and density. It evaluates tumor microvasculature on the order of 10 – 100 microns in diameter and may provide a powerful prognostic tool for the diagnosis of breast cancer, and eventually for treatment evaluation.

This is a 3-arm single center study of 45 patients. These cohorts will include 15 breast patients scheduled to undergo a biopsy, and 15 thyroid patients scheduled to undergo fine needle aspiration, biopsy, or thyroidectomy that consent to undergo CESR imaging in conjunction with b-mode ultrasound prior to their scheduled biopsy. Prior to imaging clinical patients, the third arm will include 15 healthy volunteers that will be imaged to optimize imaging parameters. Despite the similarity to our previous study, LCCC 1748, optimization is required because we will employ a new imaging technique using a different US system. The optimization includes adjusting the frame rate, power, depth of imaging, and the linear translation rate. The primary objectives of this study are to evaluate the sensitivity and specificity of CESR imaging in the analysis of known breast and thyroid lesions by comparing image analyses to the pathological results for these lesions. The secondary objectives of this study are to compare the sensitivity and specificity of CESR imaging with traditional b-mode ultrasound in the distinction of malignant versus benign breast and thyroid lesions.

1.2 Disease Background

1.2.1 Breast Cancer

Breast cancer is the most common cancer type among women. Approximately 10% of women in the United States develop breast cancer during their lifetime, and 30% to 40% of these patients will die from it.[1, 2] Mammography is an effective tool for the early detection of breast cancer in the majority of women.[3] However, for women with dense breast tissue (considered an independent risk factor for breast cancer) and younger women, mammography performs poorly due to lower sensitivity and specificity in these groups.[4] For young women with heritable mutations who wish to begin screening at a younger age, these limitations are especially problematic.[5] Additionally, mammography is less sensitive in women who have undergone breast augmentation. Given these limitations, most of these women may undergo additional imaging with breast ultrasound or Magnetic Resonance Imaging (MRI).

MRI is time consuming, extraordinarily costly, and has limited availability, especially among rural and underserved populations. Another screening option, breast ultrasound (without contrast), is widely used when additional imaging beyond mammogram is required due to its real-time imaging capability (>30 images per second), portability, safety (does not involve radiation), and relatively low cost compared to breast MRI. Unfortunately, while breast ultrasound is highly sensitive (96%), it is less specific (70%), resulting in a high false positive rate. This results in unnecessary biopsies with associated complications, additional follow-up and negative psychosocial impacts on patients, e.g., significant anxiety. A significant clinical need exists to improve breast ultrasound sensitivity and specificity.

1.2.2 **Thyroid Cancer**

The most common endocrine cancer is thyroid cancer (approximately 1.0%–1.5% of all new cancers diagnosed each year in the USA). In the United States, 53,000 people are diagnosed with thyroid cancer each year.[6] In many countries in the developed world, thyroid cancer incidence has increased dramatically over the past three decades.[7] Increased frequency in use of sensitive diagnostic procedures, including ultrasound, Doppler examination and imaging techniques like CT, MRI, or PET scanning, has amplified the detection of thyroid cancer among other cancer types.[8] However, thyroid cancer incidence and mortality tendencies have been recognized as being consistent with overdiagnosis.[9] The financial impact of overdiagnosis in a thyroid cancer patient can range from hundreds to thousands dollars. It may also cause prospective harm in standings of avoidable distress and conceivable adverse consequences of avoidable treatment. [10]

1.3 **Ultra-fast and Super-Resolution Imaging**

Recent developments in ultrasound hardware and software have enabled a substantial leap forward in ultrasound imaging technology. New programmable ultrasound systems can utilize software beamformers, parallel and distributed computing architectures, and large onboard memory to perform ultra-fast imaging, on the order of thousands of frames per second, compared to ultrasound systems still utilized in the clinic which are limited to only slightly past 30 frames per second. This 'quantum leap' in system performance has enabled several revolutionary advancements that will ensure that ultrasound in the clinic will soon offer substantial capabilities beyond what is currently available. One such novel technology is 'ultrasound localization microscopy', also referred to in this proposal as contrast enhanced super-resolution (CESR) imaging.[11] This imaging approach has been developed by researchers in the medical ultrasound domain who have made an effort to mimic the revolutionary new technology of optical localization microscopy. Optical localization

microscopy exploits the stochastic blinking of specific fluorescent sources and super-localizes the center of each source by virtue of its separability. [12, 13] By accumulating these center positions over thousands of acquisitions, the resulting image achieves a ten-fold resolution improvement and enables imaging cell membrane and small organelles with a resolution beyond the diffraction limit. In the medical ultrasound domain, different techniques have been investigated to achieve an ultrasound super resolution image, using the blinking of contrast agent microbubbles as an acoustic equivalent of the fluorescent sources. Some groups used highly diluted contrast agents to meet the key requisite of separable microbubble detection.[14, 15] Although these groups obtained super-resolved images using conventional ultrasound scanners, the long acquisition time necessary to perform diluted microbubble super resolution imaging is likely to impinge upon its practicality. Tanter's group first demonstrated the application of ultrafast acquisition and spatiotemporal filtering to separate microbubbles even at a clinically-relevant concentration, by exploiting the decorrelation of microbubbles from a stack of images.[14, 16] This technique is a direct analog to fluorescence photoactivation localization microscopy (FPALM) in optics and the acquisition time is more reasonable for clinical translation. By localizing the centers of separable scattering microbubbles, this ultrasound localization microscopy technique allows imaging of microvessels at resolutions as small as ten micrometers, over an order of magnitude smaller than the ultrasound diffraction limit. Their team has recently published the use of this novel approach in *Nature*, demonstrating super-resolved vasculature maps of rat brain slices using this super resolution contrast ultrasound technique (Fig. 2.).[11] The [name] Lab at UNC, following work from Tanter's group, has taken this approach a step further, applying it with a mechanically scanned system to obtain 3-D images of tumor-associated angiogenesis.[17] Our results illustrate that we can observe the same microvascular abnormalities we observe with Acoustic Angiography in tumors – supporting our hypothesis that we will be able to use super-resolution imaging to image cancer biomarkers in humans. It is of particular note that CESR can be performed effectively at clinical frequencies (our data to date has been acquired at 4.5 MHz with a clinical ATL probe), and depths up to 10 cm are theoretically achievable while still retaining resolution better than 100 microns, as long as microbubbles are detectable in original B mode imaging!

Another notable advantage of CESR is that it can be performed at low mechanical indices, less than 0.2, which means that it is a non-destructive imaging technique, and can readily be performed within guidelines for contrast in humans.

1.4 Software-based Ultrasound Systems

Within the last few years, computational power has finally achieved the performance required to design almost all components of an ultrasound system with dedicated programmable integrated circuits. Consequently, instead of large analog componentry with fixed capabilities, modern ultrasound systems can fit into the case of a simple PC, and still be highly programmable. Commercial vendors such as Verasonics, Cephasonics, and others, are now making programmable ultrasound systems widely available. The high-performance hardware means that these systems can transmit and receive data at rates up to the pulse repetition frequency limit based on speed of sound (thousands of frames per second, depending on tissue depth). It is this advancement which has enabled super-resolution imaging as described above.

1.5 Impact of ultrasound as a diagnostic tool

While there are clearly clinical applications for MRI, PET, SPECT, and CT that will never be supplanted by acoustics, there are clear clinical applications where ultrasound is well positioned to improve clinical outcome. For example, breast ultrasound has poor specificity and a high false positive rate, and hence it is not used as a screening tool for breast cancer. Furthermore, ultrasound is challenged to detect breast lesions smaller than a few millimeters. The same can be said about ultrasound's sensitivity to malignant thyroid and prostate cancer. Improvements in specificity in these fields would have a significant clinical impact. Furthermore, due to the low-cost and portability of the next generation of laptop or handheld-sized ultrasound systems, this modality is uniquely poised to expand diagnostic capability to rural and underserved locations and populations worldwide. Other clinical applications, such as assessing vasa vasorum in atherosclerotic plaques, or assessing angiogenesis in wound healing, may also benefit from high-resolution microvascular ultrasound imaging. Furthermore, the applications of high resolution microvascular imaging in pre-clinical cancer research are readily apparent.

1.6 Ultrasound-localization microscopy/Contrast Enhanced Super Resolution (CESR) Imaging

The methods described in this protocol are based on the novel imaging technique of Ultrasound Localization Microscopy, also called Contrast Enhanced Super-Resolution Imaging (CESR). This technology is only about five years old – with the seminal paper being published in *Nature* in 2015.[11] Its growth has been explosive because of the enormous potential – with at least 8 talks in this area at the 2016 International Ultrasonics Symposium. Further innovation from this technique arises from our 3-D CESR implementation, which has been published in November 2016.[17] In this project, we will advance this technology to the next step – fast 3-D CESR with a matrix transducer, combined with unique approaches such as multi-focus adaptive beamforming to increase

sensitivity, pushing its innovation to the next level with the goal of clinical translation.

1.7 Investigational super-resolution imaging methods

We will perform contrast enhanced super-resolution (CESR) imaging of tumors using a Verasonics Vantage system (Verasonics Inc., Redmond, WA, USA) with one of three different ultrasound probes, using plane-wave imaging at a pulse repetition frequency of 500 Hz. Two of the possible probes are 32x32 element matrix arrays with center frequencies of 1.5 and 3 MHz. The third probe is a hybrid dual-frequency array that transmits at 1.7 MHz with two single elements and receives at 20 MHz on a linear array. The transmitted pulses will be 1 cycle sinusoids at 1.5, 1.7, or 3 MHz with mechanical index less than 0.3. This low mechanical index was chosen to minimize bubble destruction under high frame rate insonification.

For data acquired with the matrix probes, a high-pass spatiotemporal singular value decomposition (SVD) filter is applied to detect the decorrelation of bubbles, yielding individual sources on the filtered images. This spatiotemporal filter can discriminate bubble signals whose spatial coherence is low from tissue signals whose spatial coherence is high because their temporal variations affect many neighboring pixels the same way.[18] For data acquired with the dual-frequency probe, bubbles are detected based on their nonlinear response relative to tissue. Hysteresis thresholding is used to localize the bubbles on the filtered images. Bubble centers are detected and center positions from all the frames are accumulated to get a super-resolution image, with a pixel size of 10 $\mu\text{m} \times 10 \mu\text{m}$, for each scan slice.

1.8 Perflutren Lipid Background and Known Toxicities

See <https://definityimaging.com/pdf/definity-pi.pdf> for full prescribing information on perflutren when used according to its FDA-approved indication.

1.8.1 Background and Current Indications

Definity® (perflutren lipid) is an FDA-approved lipid-shell microbubble ultrasound (US) contrast agent that may be administered by an intravenous (IV) bolus or infusion. Currently, this contrast agent is approved for use in patients with suboptimal echocardiograms to opacify the left ventricular chamber and to improve delineation of the left ventricular endocardial border. It is not approved as a contrast agent for microvascular imaging in the breast or for thyroid imaging.

When used according to its approved indication, the maximum dose of perflutren is administered as either two bolus doses or one single intravenous infusion.

For our study, perflutren lipid will be administered intravenously by a nurse or trained medical personnel. We will request an investigational new drug (IND) exemption at the time of the IRB application because the investigators feel this study meets the criteria of an IND exempt study.

1.8.2 Associated Toxicities

In pre-market clinical trials, 1716 subjects were evaluated with activated perflutren lipid. Of the 1716 subjects, 144 subjects (8.4%) had at least one treatment-related adverse reaction. There were 26 serious adverse events and 15 (0.9%) subjects discontinued because of an adverse event.

Nineteen subjects (1.1%) suffered serious cardiopulmonary adverse events including eight deaths. The deaths occurred several days after activated perflutren lipid administration and appear to be related to the course of underlying disease. Of the 11 other serious adverse events, which appeared within 2-15 days of the drug administration, all appeared to be a progression of underlying cardiac and non-cardiac disease.

However, a role for perflutren lipid in the initiation or course of these adverse events cannot be ruled out.

There were 15 discontinuations reported. Nine of these patients were discontinued after the first injection. One patient experienced a hypersensitivity reaction with urticaria and pruritus and all the other patients experienced dizziness, chest pain, dyspnea or back pain. Adverse events (AEs) appeared within 1 – 15 minutes of the drug administration and were of moderate intensity resolving usually without treatment within minutes or hours after onset.

For all AEs, there were no differences in the overall incidence based on age, gender, or route of administration. The most common events were (% of patients experiencing): headache (2.3%), back and renal pain (1.2%), flushing (1.1%) and nausea (1.0%).

Cardiopulmonary Reactions

In 2007, in response to post-marketing reports of 4 deaths and 190 serious cardiopulmonary reactions, the FDA issued a black box warning for both Definity® and Optison® adding disease state contraindications and a mandatory 30 minute monitoring period following administration in all patients. Following this there have been several large scale safety studies looking into the records of a total of more than 200,000 patients who received one of these contrast agents. In all those studies a composite rate of serious adverse events was calculated to be 1 – 3 in

10,000,[19] compared to gadolinium-based MRI contrast which has an incidence of NSF of 2 – 5 in 100 patients with chronic kidney disease.[20]

Following a meeting of the FDA Cardio-renal Advisory Committee in 2008, the black box warning was revised. The revisions shortened the contraindications to include cardiac shunts and hypersensitivity to perflutren, and mandated the 30 minute monitoring period be limited to patients with pulmonary hypertension or unstable cardiopulmonary conditions. The black box warning was further revised in 2011, removing the mandatory 30 minute monitoring period, but stating that most serious cardiopulmonary reactions occur within 30 minutes of administration. For this reason, the label states that cardiopulmonary resuscitation personnel and equipment be readily available prior to perflutren administration, and that all patients be monitored for acute reactions.

Patients with a history of cardiac shunts, pulmonary hypertension or unstable cardiopulmonary conditions will be excluded from our study. In addition, all patients will be monitored for 15-minute post-perflutren administration by the research nurse or research physician.

Hypersensitivity Reactions

The real risk of perflutren in our study is to the small number of potential patients with undiagnosed allergy to perflutren. Post-marketing reports have included anaphylactoid events and other serious but non-fatal adverse reactions, typically within 30 minutes of drug administration (see the package insert for additional information. In order to avoid a potentially fatal event, epinephrine will be readily accessible in the code cart in the mammography clinic.

High Ultrasound Mechanical Index (MI)

High ultrasound MI values may cause microsphere cavitation or rupture and lead to ventricular arrhythmias. In addition, end-systolic triggering with high mechanical indices has been reported to cause ventricular arrhythmias.

Use in Patients with Known Breast Lesions

US contrast agents including perflutren should carry no additional risks in patients with a known breast lesions, as they are cleared by the lungs. The phospholipid component of perflutren lipid microspheres are thought to be metabolized to free fatty acids, while the octafluoropropane (OFP), as a stable gas, is not metabolized. In a small (n=8) pharmacokinetic study in healthy subjects, OFP was undetectable after 10 minutes in most subjects either in the blood or expired air, with a mean half-life of 1.3 minutes (Definity® Prescribing Information).

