3.1.2.1 Institutionalized subject (prisoner or nursing home patient)

3.1.2.2 Critically ill or medically unstable and whose critical course during the observation period would be unpredictable (e.g., chronic obstructive pulmonary disease (COPD))

3.1.2.3 Known hypersensitivity to sulfur hexafluoride or to any component of perflutren lipid (Definity®)

3.1.2.4 Active cardiac disease including any of the following:

- Severe congestive heart failure (class IV in accordance with the classification of the New York Heart Association)
- Unstable angina.
- Severe arrhythmia (i.e. ventricular tachycardia, flutter fibrillation; ventricular premature complexes occurring close to the preceding T-wave, multifocal complexes).
- Myocardial infarction within 14 days prior to the date of proposed Definity® administration.
- Pulmonary hypertension
- Cardiac shunts

3.1.2.5 Any woman who is pregnant or has reason to believe she is pregnant or any woman who is lactating (the possibility of pregnancy has to be excluded by negative urine β -HCG results, obtained within 24 hours before the perflutren lipid administration, or on the basis of patient history, as defined by the UNC IRB SOP 4801.)

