3.2.2.2 Institutionalized subject (prisoner or nursing home patient)

3.2.2.3 Critically ill or medically unstable and whose critical course during the observation period would be unpredictable (e.g., chronic obstructive pulmonary disease (COPD))

3.2.2.4 Sonographically visible breast lesion larger than 2cm or greater than 3cm in depth from the skin surface

3.2.2.5 Known hypersensitivity to sulfur hexafluoride or to any component of perflutren lipid (Definity®)

3.2.2.6 Active cardiac disease including any of the following:

- Severe congestive heart failure (class IV in accordance with the classification of the New York Heart Association)
- Unstable angina.
- Severe arrhythmia (i.e. ventricular tachycardia, flutter fibrillation; ventricular premature complexes occurring close to the preceding T-wave, multifocal complexes).
- Myocardial infarction within 14 days prior to the date of proposed Definity® administration.
- Pulmonary hypertension
- Cardiac shunts

3.2.2.7 Any woman who is pregnant or has reason to believe she is pregnant or any woman who is lactating (the possibility of pregnancy has to be excluded by negative urine β-HCG results, obtained within 24 hours

before the perflutren lipid administration, or on the basis of patient history, as defined by the UNC IRB SOP 4801.)

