3.3.2 Exclusion Criteria

All subjects meeting any of the exclusion criteria at baseline will be excluded from study participation

[figure not shown]
- 3.3.2.1 Institutionalized subject (prisoner or nursing home patient)
- 3.3.2.2 Critically ill or medically unstable and whose critical course during the observation period would be unpredictable (e.g., chronic obstructive pulmonary disease (COPD))
- 3.3.2.3 Known hypersensitivity to sulfur hexafluoride or to any component of perflutren lipid (Definity®)
- 3.3.2.4 Active cardiac disease including any of the following:
 - Severe congestive heart failure (class IV in accordance with the classification of the New York Heart Association)
 - Unstable angina.
 - Severe arrhythmia (i.e. ventricular tachycardia, flutter fibrillation; ventricular premature complexes occurring close to the preceding T-wave, multifocal complexes).
 - Myocardial infarction within 14 days prior to the date of proposed Definity® administration.
 - Pulmonary hypertension
 - Cardiac shunts

3.3.2.5 Any woman who is pregnant or has reason to believe she is pregnant or any woman who is lactating (the possibility of pregnancy has to be excluded by negative urine β -HCG results, obtained within 24 hours before the perflutren lipid administration, or on the basis of patient history, as defined by the UNC IRB SOP 4801.)

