6.1.1 Known and Associated Risks

For indication see <https://www.definityimaging.com/pdf/definity-pi.pdf> and see section 1.8.2 for a summary of toxicities reported in clinical trials. In addition, the following warnings and precautions are noted in the January 2017 labeling:

Serious Cardiopulmonary Reactions:

Serious cardiopulmonary reactions including fatalities have occurred uncommonly during or shortly following perflutren-containing microsphere administration, typically within 30 minutes of administration. The risk for these reactions may be increased among patients with unstable cardiopulmonary conditions (acute myocardial infarction, acute coronary artery syndromes, worsening or unstable congestive heart failure, or serious ventricular arrhythmias). Always have cardiopulmonary

resuscitation personnel and equipment readily available prior to Definity® administration and monitor all patients for acute reactions. The reported reactions include: fatal cardiac or respiratory arrest, shock, syncope, symptomatic arrhythmias (atrial fibrillation, tachycardia, bradycardia, supraventricular tachycardia, ventricular fibrillation, ventricular tachycardia), hypertension, hypotension, dyspnea, hypoxia, chest pain, respiratory distress, stridor, wheezing, loss of consciousness, and convulsions.

Hypersensitivity Reactions:

In postmarketing use, serious hypersensitivity reactions were observed during or shortly following perflutren-containing microsphere administration including: Shock, bronchospasm, throat tightness, angioedema, edema (pharyngeal, palatal, mouth, peripheral, localized), swelling (face, eye, lip, tongue, upper airway), facial hypoesthesia, rash, urticaria, pruritus, flushing, and erythema have occurred in patients with no prior exposure to perflutren-containing microsphere products. Always have cardiopulmonary resuscitation personnel and equipment readily available prior to Definity® administration and monitor all patients for hypersensitivity reactions.

Systemic Embolization of Perflutren in Patients with Cardiac Shunts:

When administering Definity® to patients with a cardiac shunt, the microspheres can bypass filtering by the lung and enter the arterial circulation. Assess patients with shunts for embolic phenomena following Definity® administration. Definity® is only for intravenous administration; do not administer Definity® by intra-arterial injection.

Ventricular Arrhythmia Related to High Mechanical Index:

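### Section 1.8.2 excludes a history of unstable cardiopulmonary conditions, but section 3 sets narrower limits and leaves some past events and heart failure below class IV to a two-part general criterion

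*Combined protocol and SAP*

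**What the plan says.** Section 1.8.2 (Associated Toxicities), in its discussion of cardiopulmonary reactions, states: "Patients with a history of cardiac shunts, pulmonary hypertension or unstable cardiopulmonary conditions will be excluded from our study". It does not define the last of the three categories.

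Section 6.1.1 (Known and Associated Risks) reproduces label warnings and is the one place where the category is spelled out: "unstable cardiopulmonary conditions (acute myocardial infarction, acute coronary artery syndromes, worsening or unstable congestive heart failure, or serious ventricular arrhythmias". It says that the risk of serious reactions may be higher in these patients.

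Section 3 carries the exclusion through two separate criteria, worded alike in every arm.

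- **General criterion** (3.1.2.2, 3.2.2.3, 3.3.2.2): "Critically ill or medically unstable and whose critical course during the observation period would be unpredictable (e.g., chronic obstructive pulmonary disease (COPD".
- **Cardiac criterion** (3.1.2.4, 3.2.2.6, 3.3.2.4): a list under the heading of active cardiac disease. It includes "Severe congestive heart failure (class IV in accordance with the classification of the New York Heart Association", unstable angina, severe arrhythmia, "Myocardial infarction within 14 days prior to the date of proposed Definity® administration", pulmonary hypertension and cardiac shunts.

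One criterion is enough: "All subjects meeting any of the exclusion criteria at baseline will be excluded from study participation".

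**The concern.** The safety section and the eligibility section describe the excluded group in different terms. Section 1.8.2 speaks of history, while the cardiac list in section 3 speaks of active disease. Section 6.1.1 describes heart failure by its course (worsening or unstable), while section 3 describes it by functional class.

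The question is who may receive contrast. Section 4.2.1 has research staff identify eligible patients, and section 10.4 allows no exceptions to eligibility, so the criteria need one meaning. Directly after its exclusion sentence and a statement on monitoring, section 1.8.2 goes on to present undiagnosed allergy as the study's real risk from the agent. That account presupposes that the cardiopulmonary risk group is absent. The agent is used outside its approved indication (1.8.1), and the research images do not inform care (4.2.2.2).

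**Working it through.** No figure is at issue, so the check sets the passages side by side. The result is the same in all three arms.

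| Condition in 1.8.2 or 6.1.1 | Match in section 3 | Result |
|---|---|---|
| Cardiac shunts | Named, no time limit | Covered |
| Pulmonary hypertension | Named, no time limit | Covered |
| Acute myocardial infarction | Infarction within 14 days | Current event covered; older event not named |
| Acute coronary syndromes | Unstable angina, plus recent infarction | Current event covered; past event not named |
| Serious ventricular arrhythmias | "Severe arrhythmia (i.e. ventricular tachycardia, flutter fibrillation" and further items | Current event covered; past event not named |
| Worsening or unstable heart failure | Class IV named | Lower classes reached only through the general criterion |
| Unstable pulmonary disease | General criterion, with COPD as its example | Reachable |

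Every category thus has some counterpart in section 3. The mismatch is one of scope, and two cases show it.

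**Case 1: a past event, now stable.** Take an infarction three weeks ago, which is 21 days and so outside the 14-day limit, in a patient who is now stable. If the word history in 1.8.2 governs all three categories, and 6.1.1 supplies the meaning of the third, 1.8.2 excludes this patient. The infarction item does not. The general criterion does not either, because it concerns patients who are unstable now.

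**Case 2: worsening heart failure below class IV.** Take a patient with recently worsening class III heart failure who attends for an outpatient biopsy. Section 6.1.1 includes "worsening or unstable congestive heart failure, or serious ventricular arrhythmias" among the unstable conditions, so 1.8.2 read with 6.1.1 excludes the patient. The heart-failure item in section 3 does not, because it stops at class IV. What remains is the general criterion, which has two parts joined by *and*: the patient must be critically ill or unstable, and the critical course over the observation period must be unpredictable. The criterion does not define that period. It could be the 15 minutes of monitoring (4.2.2.1), the 30 days of event recording (8.2, 8.3.1) or the 6 months of chart follow-up (4.2). An unconditional exclusion in 1.8.2 has become a judgement in section 3.

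**The case against.** The strongest reply is that the two sections can be read together. Every arm has a general instability criterion that works independently of the cardiac list and may well catch many currently unstable patients, including some with heart failure below class IV. Section 1.8.2 is itself protocol text and section 10.4 requires adherence to the protocol, so staff who exclude under either section breach neither. The list in 6.1.1 is label wording and is not offered as the study's definition. The word history may attach to shunts alone. Arm 1 consists of healthy volunteers, in whom these conditions are unlikely. All participants are observed after contrast, with resuscitation staff and equipment at hand.

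Much of this stands, and it rules out two stronger readings. A reader might infer that section 3 reaches nothing beyond class IV heart failure and selected cardiac events, so that patients whom 1.8.2 excludes will receive contrast. The documents do not support that: shunts and pulmonary hypertension are named, the general criterion applies in every arm, and nothing says an investigator would pass a worsening class III patient under it. A reader might also infer that unstable pulmonary disease is missed. It is not, since COPD is the general criterion's own example.

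The reply does not remove the two cases above. The general criterion cannot reach a past event in a stable patient, and for heart failure below class IV it asks for more than 1.8.2 does. That 6.1.1 may not be the study's definition leaves the phrase in 1.8.2 with no definition at all. Observation and resuscitation cover reduce the harm from a reaction but do not settle who is eligible.

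**Conclusion.** The point holds as an inconsistency of scope. Patients with a past unstable event outside the section 3 limits, and patients with worsening heart failure below class IV who are not judged to meet both parts of the general criterion, are excluded on the ordinary reading of 1.8.2 but not clearly by section 3.

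The conclusion rests on two assumptions: that history in 1.8.2 applies to all three categories, and that 6.1.1 shows what the protocol means by unstable cardiopulmonary conditions. If the first fails, Case 1 falls away and Case 2 remains. If the second fails, 1.8.2 relies on an undefined term, which also needs correction.

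The same wording governs all 45 planned participants, but the documents give no basis for counting those affected. The number is unknown and probably small, least likely to arise among the 15 healthy volunteers. The documents do not show that anyone has received or will receive contrast against the intent of 1.8.2.

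**What to change.** Reconcile section 1.8.2, section 6.1.1 and the paired criteria 3.1.2.2/3.1.2.4, 3.2.2.3/3.2.2.6 and 3.3.2.2/3.3.2.4, so that one definition of the excluded cardiopulmonary conditions applies throughout. Three things should agree:

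- the qualifier, either history or active, and which conditions it governs;
- the heart-failure wording;
- how the general criterion relates to the cardiac list, including what its observation period is.

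The investigator and the IRB should decide which definition holds; this review proposes none. The cost is a wording amendment, either to the parallel criteria in three arms or to the sentence in 1.8.2, with 6.1.1 cross-referenced. It needs IRB approval before implementation (section 10.5). Few candidates are likely to change status, and neither the planned numbers nor the analysis needs to change.
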